17.1.3 Treatment Exposure

Table 25: Summary of Early Treatment Terminations by Site

	Site 1 (N=XX)	Site 2 (N=XX)	Site 3 (N=XX)	Site 4 (N=XX)	Total (N=XX)
Number of early study treatment terminations ¹	N (X.X%)				
Reason for early treatment termination ²					
Participant became pregnant	N (X.X%)				
Participant unable to tolerate side effects					
Participant deceased					
Participant withdrew consent					
Participant continued to experience intolerable effects after a dose reduction					
Contraindicated concomitant medication					
Participant refused, non-specific					
Participant left study and never returned					
Clinical deterioration: new onset of psychiatric or medical condition					
Physical illness or condition that precludes study intervention					
Participant feels study intervention no longer necessary, cured					
Participant feels study intervention no longer necessary, not working					
Participant terminated early from study					
Other					

¹ Percentage is out of the total number of participants randomized.

² Percentages are out of the total number of early treatment terminations.

Table 26: Summary of Early Treatment Terminations by Treatment Arm

	Treatment Arm		
	Sham (N=XX)	rTMS (N=XX)	Total (N=XX)
Percent of early study treatment terminations ¹	N (X.X%)		
Reason for early treatment termination ²			
Participant became pregnant	N (X.X%)		
Participant unable to tolerate side effects			
Participant deceased			
Participant withdrew consent			
Participant continued to experience intolerable effects after a dose reduction			
Contraindicated concomitant medication			
Participant refused, non-specific			
Participant left study and never returned			
Clinical deterioration: new onset of psychiatric or medical condition			
Physical illness or condition that precludes study intervention			
Participant feels study intervention no longer necessary, cured			
Participant feels study intervention no longer necessary, not working			
Participant terminated early from study			
Other			

¹ Percentage is out of the total number of participants randomized.

² Percentages are out of the total number of early treatment terminations.

Table 27: Summary of Early Treatment Terminations by Primary Substance of Use

	Primary Substance of Use		Total (N=XX)
	Cocaine (N=XX)	Methamphetamine (N=XX)	
Percent of early study treatment terminations ¹	N (X.X%)		
Reason for early treatment termination ²			
Participant became pregnant	N (X.X%)		
Participant unable to tolerate side effects			
Participant deceased			
Participant withdrew consent			
Participant continued to experience intolerable effects after a dose reduction			
Contraindicated concomitant medication			
Participant refused, non-specific			
Participant left study and never returned			
Clinical deterioration: new onset of psychiatric or medical condition			
Physical illness or condition that precludes study intervention			
Participant feels study intervention no longer necessary, cured			
Participant feels study intervention no longer necessary, not working			
Participant terminated early from study			
Other			

¹ Percentage is out of the total number of participants randomized.

² Percentages are out of the total number of early treatment terminations.

Table 28: Summary of Treatment Exposure by Site

Study Week ¹		Site 1 (N=XX)	Site 2 (N=XX)	Site 3 (N=XX)	Site 4 (N=XX)	Total (N=XX)
Week 1	Number of rTMS sessions performed ²					
	N	XX				
	Mean	XX.X				
	SD	XX.XX				
	Min	XX				
	25th percentile	XX				
	Median	XX				
	75th percentile	XX				
	Max	XX				
...						
Week 8	...					
Overall	...					

¹ Study Week refers to the week as indicated by the study visit number.

² An rTMS session is considered performed if the rTMS Intervention (TMS) form indicates as such.

Table 29: Summary of Treatment Exposure by Treatment Arm

Study Week ¹		Treatment Arm		Total (N=XX)
		Sham (N=XX)	rTMS (N=XX)	
Week 1	Number of rTMS sessions performed ²			
	N	XX		
	Mean	XX.X		
	SD	XX.XX		
	Min	XX		
	25th percentile	XX		
	Median	XX		
	75th percentile	XX		
	Max	XX		
...				
Week 8	...			
Overall	...			

¹ Study Week refers to the week as indicated by the study visit number.

² An rTMS session is considered performed if the rTMS Intervention (TMS) form indicates as such.

Table 30: Summary of Treatment Exposure in Participants with rTMS Session Threshold Met¹ by Treatment Arm

		Treatment Arm		Total (N=XX)
Study Week ²		Sham (N=XX)	rTMS (N=XX)	
Week 1	Number of rTMS sessions performed ³			
	N	XX		
	Mean	XX.X		
	SD	XX.XX		
	Min	XX		
	25th percentile	XX		
	Median	XX		
	75th percentile	XX		
	Max	XX		
...				
Week 8	...			
Overall	...			

¹ Participants met the rTMS session threshold if they completed at least 20 rTMS sessions.

² Study Week refers to the week as indicated by the study visit number.

³ An rTMS session is considered performed if the rTMS Intervention (TMS) form indicates as such.

Table 31: Summary of Treatment Exposure in Participants with rTMS Session Performed during Week 8 by Treatment Arm

		Treatment Arm		Total (N=XX)
Study Week ¹		Sham (N=XX)	rTMS (N=XX)	
Week 1	Number of rTMS sessions performed ²			
	N	XX		
	Mean	XX.X		
	SD	XX.XX		
	Min	XX		
	25th percentile	XX		
	Median	XX		
	75th percentile	XX		
	Max	XX		
...				
Week 8	...			
Overall	...			

¹ Study Week refers to the week as indicated by the study visit number.

² An rTMS session is considered performed if the rTMS Intervention (TMS) form indicates as such.

Table 32: Summary of Engagement in rTMS Sessions by Treatment Arm

		Treatment Arm		Total (N=XX)
Study Week ¹		Sham (N=XX)	rTMS (N=XX)	
Week 1	Number of rTMS Sessions ²			
	Attended	N		
	Initiated and stopped prematurely	N (X.X%)		
	Performed	N (X.X%)		
...	...			
Week 8	...			
Overall				

¹ Study Week refers to the week as indicated by the study visit number.

² rTMS session attendance, whether the session was stopped prematurely, and whether the session was performed was captured on the rTMS Intervention (TMS) form. Percentages are calculated based on the denominator of the number of attended sessions.

[figure not shown]
Table 33: Summary of Engagement in rTMS Sessions by Primary Substance of Use

Study Week ¹		Primary Substance of Use		Total (N=XX)
		Cocaine (N=XX)	Methamphetamine (N=XX)	
Week 1	Number of rTMS Sessions ²			
	Attended	N		
	Initiated and stopped prematurely	N (X.X%)		
	Performed	N (X.X%)		
...	...			
Week 8	...			
Overall				

¹ Study Week refers to the week as indicated by the study visit number.

² rTMS session attendance, whether the session was stopped prematurely, and whether the session was performed was captured on the rTMS Intervention (TMS) form. Percentages are calculated based on the denominator of the number of attended sessions.

Figure 4: Average Number of rTMS Sessions Attended by Treatment Arm and Week

Example figure provided.

17.1.4 Primary Outcome

Table 34: Summary of Primary Outcome Analysis

Number of Participants Randomized	Number of Sessions Performed Per Participant ¹ Mean (SD)	Results ³		
		Number of Participants with at Least 20 Sessions ^{1,2} N (%)	95% Lower Confidence Limit	95% Upper Confidence Limit
N	X.X (X.XX)	N (XX.X%)	XX.XX%	XX.XX%

¹ A rTMS or sham session was considered performed if indicated as such on the rTMS Intervention (TMS) form.

² Percentage is calculated out of the total number of participants randomized.

³ Results are obtained by the Wilson method.

17.1.5 Supportive Analyses of the Primary Outcome

Table 35: Summary of Primary Outcome by Sex					
Subgroup	Number of Participants Randomized	Number of Sessions Performed Per Participant ¹ Mean (SD)	Results ³		
			Number of Participants with at Least 20 Sessions ^{1,2} N (%)	95% Lower Confidence Limit	95% Upper Confidence Limit
Male	N	X.X (X.XX)	N (XX.X%)	XX.XX%	XX.XX%
Female					

¹ A rTMS or sham session was considered performed if indicated as such on the rTMS Intervention (TMS) form.

² Percentage is calculated out of the total number of participants randomized.

³ Results are obtained by the Wilson method within the subgroup.

Table 36: Summary of Primary Outcome by Race					
Subgroup	Number of Participants Randomized	Number of Sessions Performed Per Participant ¹ Mean (SD)	Results ³		
			Number of Participants with at Least 20 Sessions ^{1,2} N (%)	95% Lower Confidence Limit	95% Upper Confidence Limit
Black	N	X.X (X.XX)	N (XX.X%)	XX.XX%	XX.XX%
White					
Other ⁴					

¹ A rTMS or sham session was considered performed if indicated as such on the rTMS Intervention (TMS) form.

² Percentage is calculated out of the total number of participants randomized.

³ Results are obtained by the Wilson method within the subgroup.

⁴ Other includes American Indian or Alaska Native, Native Hawaiian or Pacific Islander, Other, and Multiple Race. Missing or refused responses are not included in the analysis (N=X).

Table 37: Summary of Primary Outcome by Ethnicity					
Subgroup	Number of Participants Randomized	Number of Sessions Performed Per Participant ¹ Mean (SD)	Results ³		
			Number of Participants with at Least 20 Sessions ^{1,2} N (%)	95% Lower Confidence Limit	95% Upper Confidence Limit
Not Hispanic or Latinx	N	X.X (X.XX)	N (XX.X%)	XX.XX%	XX.XX%
Hispanic or Latinx					

¹ A rTMS or sham session was considered performed if indicated as such on the rTMS Intervention (TMS) form.

² Percentage is calculated out of the total number of participants randomized.

³ Results are obtained by the Wilson method within the subgroup.

Table 38: Summary of Primary Outcome by Age

Subgroup	Number of Participants Randomized	Number of Sessions Performed Per Participant ¹ Mean (SD)	Results ³		
			Number of Participants with at Least 20 Sessions ^{1,2} N (%)	95% Lower Confidence Limit	95% Lower Confidence Limit
18-44 years	N	X.X (X.XX)	N (XX.X%)	XX.XX%	XX.XX%
45 years or greater					

¹ A rTMS or sham session was considered performed if indicated as such on the rTMS Intervention (TMS) form.

² Percentage is calculated out of the total number of participants randomized.

³ Results are obtained by the Wilson method within the subgroup.

Table 39: Summary of Primary Outcome by Employment Status

Subgroup	Number of Participants Randomized	Number of Sessions Performed Per Participant ¹ Mean (SD)	Results ³		
			Number of Participants with at Least 20 Sessions ^{1,2} N (%)	95% Lower Confidence Limit	95% Lower Confidence Limit
Employed ⁴	N	X.X (X.XX)	N (XX.X%)	XX.XX%	XX.XX%
Unemployed					
Other ⁵					

¹ A rTMS or sham session was considered performed if indicated as such on the rTMS Intervention (TMS) form.

² Percentage is calculated out of the total number of participants randomized.

³ Results are obtained by the Wilson method within the subgroup.

⁴ Employed includes working now, temporarily laid off, sick leave, or maternity leave.

⁵ Other includes retired, disabled (permanently or temporarily), keeping house, student, and other. Missing or refused responses are not included in the analysis (N=X).

Table 40: Summary of Primary Outcome Analysis by Primary Substance of Use

Primary Substance of Use	Number of Participants Randomized	Number of Sessions Performed Per Participant ¹ Mean (SD)	Results ³			
			Number of Participants with at Least 20 Sessions ^{1,2} N (%)	95% Lower Confidence Limit	95% Lower Confidence Limit	p-value
Cocaine	N	X.X (X.XX)	N (XX.X%)	XX.XX%	XX.XX%	0.xxx
Methamphetamine						

¹ A rTMS or sham session was considered performed if indicated as such on the rTMS Intervention (TMS) form.

² Percentage is calculated out of the total number of participants randomized.

³ Confidence limits results are obtained by the Wilson method within the primary substance of use. P-value is obtained from the Fisher's exact test.

Table 41: Summary of Primary Outcome Analysis by Treatment Arm

Treatment Arm	Number of Participants Randomized	Number of Sessions Performed Per Participant ¹ Mean (SD)	Results ³			
			Number of Participants with at Least 20 Sessions ^{1,2} N (%)	95% Lower Confidence Limit	95% Lower Confidence Limit	p-value
Sham	N	X.X (X.XX)	N (XX.X%)	XX.XX%	XX.XX%	0.xxx
rTMS						

¹ A rTMS or sham session was considered performed if indicated as such on the rTMS Intervention (TMS) form.

² Percentage is calculated out of the total number of participants randomized.

³ Confidence limits results are obtained by the Wilson method within the treatment arm. P-value is obtained from the Fisher's exact test.

Table 42: Summary of Primary Outcome Analysis by Primary Substance of Use and Treatment Arm

Primary Substance of Use	Treatment Arm	Number of Participants Randomized	Number of Sessions Performed Per Participant ¹ Mean (SD)	Results ³		
				Number of Participants with at Least 20 Sessions ^{1,2} N (%)	95% Lower Confidence Limit	95% Lower Confidence Limit
Cocaine	Sham	N	X.X (X.XX)	N (XX.X%)	XX.XX%	XX.XX%
	rTMS					
Methamphetamine	Sham					
	rTMS					

¹ A rTMS or sham session was considered performed if indicated as such on the rTMS Intervention (TMS) form.

² Percentage is calculated out of the total number of participants randomized.

³ Confidence limits results are obtained by the Wilson method within the primary substance of use and treatment arm.

Table 43: Primary Outcome Analysis by Primary Substance of Use and Treatment Arm: Conditional Results

Variable of Interest	Conditional Variable	Results ³	
		Number of Participants with at Least 20 Sessions ^{1,2} N (%)	p-value
Primary Substance of Use: Cocaine	Treatment Arm: Sham	N (XX.X%)	0.xxx
	Treatment Arm: rTMS		
Primary Substance of Use: Methamphetamine	Treatment Arm: Sham		
	Treatment Arm: rTMS		
Treatment Arm: Sham	Primary Substance of Use: Cocaine		
	Primary Substance of Use: Methamphetamine		
Treatment Arm: rTMS	Primary Substance of Use: Cocaine		
	Primary Substance of Use: Methamphetamine		

¹ A rTMS or sham session was considered performed if indicated as such on the rTMS Intervention (TMS) form.

² Percentage is calculated out of the total number of participants randomized.

³ P-value results are obtained from the Fisher's exact test for independence of the outcome and the variable of interest conditional on the given variable.

Table 44: Summary of Primary Outcome Analysis by Site

[figure not shown]
Site	Number of Participants Randomized	Number of Sessions Performed Per Participant ¹ Mean (SD)	Results ³		
			Number of Participants with at Least 20 Sessions ^{1,2} N (%)	95% Lower Confidence Limit	95% Lower Confidence Limit
Site 1	N	X.X (X.XX)	N (XX.X%)	XX.XX%	XX.XX%
Site 2					
Site 3					
Site 4					

¹ A rTMS or sham session was considered performed if indicated as such on the rTMS Intervention (TMS) form.

² Percentage is calculated out of the total number of participants randomized.

³ Results are obtained by the Wilson method within the site.

Figure 5: Forest Plot of Primary Outcome Results

Example figure provided.

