15.5 Types of Analyses

15.5.1 Additional Feasibility Analysis

The primary analysis method used for the primary (feasibility) outcome will be completed over all 160 participants. Additional analysis may include estimating the feasibility outcome percentage separately for both CUD and MUD participants, separately for real and sham rTMS, as well as separately for the four combinations of the two factors. Testing may be performed using fisher's exact test at an 0.05 significance level to determine if there are differences in the percentages across or within the factors, though emphasis is placed on estimation and 95% confidence intervals.

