7.3 Supportive Analyses of the Primary Outcome Measure

7.3.1 Demographic Subgroup Analyses

Per NIH policy (NIH, 2016), subgroup analyses will be implemented to assess whether sex at birth (Male, Female), race (Black, White, Other), ethnicity (Hispanic/Latinx, Not Hispanic/Latinx), age (18-44 years, 45 years or greater), and employment status (Employed, Unemployed, Other) are feasibility or effect modifiers. Responses missing, "Don't know," and "Refused to answer" will not be analyzed. The primary outcome percentage will be estimated in each demographic subgroup. Results will be summarized similar to the primary outcome, including a forest plot.

The corresponding SAS code is provided below:

```
proc freq data = data;
  where subgroup = x;
  table y / binomial(level = 2 cl = wilson);
run;
```

where:

- data is a dataset with one row per participant,
- subgroup is the demographic variable of interest,
- x is the subgroup level of interest, and
- y is the binary variable indicating whether the participant received at least 20 rTMS treatment sessions (y = 1) or not (y=0).

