7.3.2 Additional Feasibility Analyses

Additional analyses may include estimating the feasibility outcome percentage in the ITT population separately for both CUD and MUD participants, separately for real and sham rTMS, as well as separately for the four combinations of the two factors. A one-sided hypothesis test may be performed using Fisher's exact test at an 0.05 significance level to determine if there are differences in the percentages across or within the factors, though emphasis is placed on estimation and 95% confidence intervals. Summaries of the primary outcome by treatment arm and site and by primary substance of use (cocaine or methamphetamine) will be presented as well as a forest plot. SAS code similar to the demographic subgroup analyses can be used for the confidence intervals. The Fisher's exact test p-value SAS code is provided below:

```
proc freq data = data;
    tables y * x / chisq;
run;
```

where:

- data is a dataset with one row per participant,
- y is the binary variable indicating whether the participant received at least 20 rTMS treatment sessions, and
- x is the binary variable of interest (e.g., treatment arm or SUD).

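### The SAP sets out to judge whether five demographic factors modify feasibility, but no feasibility table gives a between-group difference with its interval

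*SAP*

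**What the plan says.** **Demographic factors.** SAP 7.3.1 names five factors and asks whether sex, race, ethnicity, age and "employment status (Employed, Unemployed, Other) are feasibility or effect modifiers". For feasibility, the analysis that follows is: "The primary outcome percentage will be estimated in each demographic subgroup". The code is a PROC FREQ filtered to one level at a time. In SAP 17.1.5, Tables 35-39 show the number randomized, mean sessions, the percentage with at least 20 sessions and 95% limits; the footnote reads "Results are obtained by the Wilson method within the subgroup".

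**Drug and arm.** SAP 7.3.2 provides for estimates by primary substance, by arm and by the four combinations. It adds: "A one-sided hypothesis test may be performed using Fisher's exact test at an 0.05 significance level", "though emphasis is placed on estimation and 95% confidence intervals". Protocol 15.5.1 has the same optional test without stating sidedness: "Testing may be performed using fisher's exact test at an 0.05 significance level". Tables 40 and 41 have a Fisher p-value column beside the within-group limits ("Confidence limits results are obtained by the Wilson method within the treatment arm" in Table 41). Table 43 gives Fisher p-values for arm within drug and drug within arm. Tables 42 (four cells) and 44 (site) have within-group limits only.

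**Forest plot.** Figure 5 is not reproduced. SAP 7.2 describes it as plotting the estimated percentage and its interval.

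**The concern.** Whether a factor modifies feasibility is a question about a difference between groups. For the demographic factors, neither the code nor the tables produce one. A reader who wants the answer must compare two separate 95% intervals, and the natural rule, that overlap means no difference, is not a 5% comparison.

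For drug and arm, the p-value answers only whether a difference was detected. It does not say how large a difference remains possible, which is what a section that puts estimation first should report.

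The trial is a feasibility pilot, and Protocol 2.5 says its feasibility results will inform the decision on a larger trial. Whether one group completes treatment less often, or active stimulation is harder to complete than sham, bears on that trial's design.

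**Working it through.** **Inputs.** From the SAP: target 160, with 80 per drug and 1:1 allocation, so about 80 per arm (2.2.1); goal rate 75% (10.1); no missing primary outcome by definition (7.9). Assumed: demographic group sizes, observed counts and true rates. The SAP gives no demographic group sizes. The 107 v 53 split used below is a two-to-one division of 160, close to the national male/female percentages in Protocol Table 3 (68/32 for cocaine, 64/36 for methamphetamine).

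**1. Reproduce the plan's precision.** The Wilson halfwidth is z·√(p(1−p)/n + z²/4n²) / (1 + z²/n), with z = 1.96. Averaged over Binomial(n, 0.75), it is 0.0663 at n=160 and 0.0927 at n=80. SAP Table 2 prints 0.066 and 0.093, so the figures agree.

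**2. What each table contains.**

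| Tables | Comparison | Within-group CI | p-value | Difference with CI |
|---|---|---|---|---|
| 35-39 | five demographic factors | yes | no | no |
| 40, 41 | drug; arm | yes | Fisher | no |
| 42, 44 | drug by arm; site | yes | no | no |
| 43 | arm within drug; drug within arm | no | Fisher | no |

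**3. One demographic example.** Take 89/107 (83.2%, Wilson 75.0 to 89.1) and 36/53 (67.9%, Wilson 54.5 to 78.9). The intervals overlap from 75.0 to 78.9. The Newcombe interval uses the same limits (l, u):

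- difference d = 0.8318 − 0.6792 = 0.1525
- lower = d − √((p₁−l₁)² + (u₂−p₂)²) = 0.1525 − √(0.0821² + 0.1098²) = 0.1525 − 0.1371 = 0.0154
- upper = d + √((u₁−p₁)² + (p₂−l₂)²) = 0.1525 + √(0.0591² + 0.1341²) = 0.1525 + 0.1465 = 0.2990

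The difference is 15.3 points, 95% CI 1.5 to 29.9. It excludes zero although the separate intervals overlap.

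**4. How often this happens.** Sum the product of the two binomial probabilities over every pair of counts that meets each criterion.

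| Group sizes | True rates | Wilson intervals separate | Newcombe CI excludes 0 |
|---|---|---|---|
| 107 v 53 | 80% v 60% | 47% | 76% |
| 107 v 53 | 80% v 65% | 24% | 54% |
| 80 v 80 | 80% v 60% | 50% | 80% |
| 80 v 80 | 83% v 67% | 33% | 65% |
| 80 v 80 | 75% v 75% | 0.5% | 4.9% |

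In the first row, the intervals overlap while the difference interval excludes zero in 76 − 47 = 29% of trials. The last row shows why: non-overlap works at a 0.5% false-positive rate, not 5%.

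**5. Drug and arm.** Suppose both arms have 60/80 (75.0%, Wilson 64.5 to 83.2). Two-sided Fisher gives p=1.00. The Newcombe limits are ±√(0.1048² + 0.0819²) = ±0.133, so −13.3 to +13.3 points. At 45/60 in each arm, the size if enrolment reached the N=120 considered in SAP 11.1.1, they are ±15.3 points.

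**The case against.** **A stronger reading a reader might infer** is that the drug and arm tables also offer nothing but separate intervals, so real differences there would pass unseen. The documents do not support it, because Tables 40, 41 and 43 carry Fisher p-values. For example, 64/80 v 51/80 has overlapping Wilson intervals (70.0 to 87.3 and 52.8 to 73.4) and a difference of 16.3 points (2.3 to 29.4), and Table 40 or 41 would show it at p=0.034 two-sided or 0.017 one-sided. At 80 per group and 80% v 60%, two-sided Fisher detects the difference in 74.5% of trials against 80% for Newcombe, so little detection is lost. What is missing there is the effect size with its interval. The test is also optional, and 7.3.2 makes it one-sided without naming a direction.

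**No document adopts an overlap rule.** That is true, and misreading by overlap is a prediction about readers. Protocol 15.7.1 has the primary percentage estimated in subgroups and the secondary outcome tested with interactions. SAP 7.2 has no hypothesis test for the primary outcome and SAP 9.0 plans none. Descriptive feasibility subgroups may therefore be deliberate. But a difference with its interval is estimation and needs no test, and 7.3.1 does pose the modifier question for feasibility.

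**Readers could work it out.** This also stands: the Newcombe interval is built from the percentages and limits the tables already print. That makes the omission easy to repair, but the SAP's own tables should still answer its question.

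**More contrasts mean more chance findings.** The demographic tables would hold seven contrasts (sex, ethnicity and age one each; race and employment two each). If they were independent, the chance of at least one false exclusion of zero would be 1 − 0.95⁷ = 30%. That calls for a label and cautious reading; it does not justify leaving the differences out.

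**Conclusion.** The concern holds for the demographic tables and, more narrowly, for drug and arm. Tables 35-39 cannot answer the modifier question in SAP 7.3.1 except by eye. Under the two-to-one split and 80% v 60%, judging by non-overlap would detect the difference in 47% of trials rather than 76%. For drug and arm, the plan gives a p-value without the estimate that 7.3.2 says it emphasises, and a p-value of 1.00 at 60/80 per arm would leave differences of about 13 points either way open.

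These sizes rest on assumed splits and rates; achieved groups may be smaller or less balanced, which would widen the difference intervals. Nothing here makes a planned analysis invalid. These are supportive analyses, and the primary percentage with its Wilson interval is unaffected. The change is worth making because it costs little and lets the plan answer its own question.

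**What to change.** - In Tables 35, 37, 38, 40 and 41, add a column with the difference in the percentage reaching 20 sessions and its Newcombe 95% CI (PROC FREQ, RISKDIFF with CL=NEWCOMBE).
- In Tables 36 and 39 (race, employment), give differences against one named reference level.
- Add a sentence to SAP 7.3 that any statement about feasibility modifiers or arm differences rests on these intervals, not on overlap or a p-value alone.
- Label the contrasts descriptive, unadjusted for multiplicity and added after database lock. SAP version 2.0 already post-dates the lock (7.10 and 14.0).

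The cost is a short SAP addition, one table column and a few lines of SAS, with no new data. The small downside is several unadjusted intervals and wider tables.
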